Study Design. C3FIT is a multicenter, randomized, single blinded, Phase III, cluster randomized trial. Sites will be stratified by patient admission volume and geographic location; subsequently, each site will be randomized to one of two patient care management strategies: the CSC/PSC versus ISPU model.

Outcomes. C3FIT’s primary outcomes are the SIS and smRS at 12 months.

Sample Size and Population. Based on the primary outcome, the study was originally designed for a total sample size of approximately 1800 patients, with approximately 18 sites. However, due to the challenges of the COVID-19 pandemic the sample size was decreased to 1,262 and the number of sites were increased to 22. The Statistical and Data Coordinating Center (SDCC) at the University of Alabama determined the change in sample size would not influence the study statistical measures and/or study power, and our funder, PCORI, approved of the changes.

Interventions. Coordinated care (including in-home/in-patient rehabilitation and skilled nursing or extended care facility visits) will be provided based on protocol-based coordination of post-acute in-home/facility care for ISPU Site patients, while CSC/PSC patients will be managed per standard CSC/PSC protocol with no additional study related management post discharge. Clinical site personnel will be provided with training specific to the arm to which they are randomized.

Duration. Patients will be followed at the site level for one year after enrollment.

1. **STUDY OBJECTIVES**

The current standard of stroke care is the JC-certified CSC/PSC care system, a collection of proven individual processes of care, but a system that lacks coordination for the post-stroke care of patients. The C3FIT trial serves as the opportunity to assess potential impact on patient QOL and functional outcomes resulting from the improved integration of care provided by the ISPU approach.

C3FIT's overall goal is to assess if patient outcomes are improved when the CSC/PSC system is supplemented with an Integrated Stroke Practice Unit (ISPU) system of care, a patient-centric model of care involving the patient and caregiver/family that coordinates care from the acute management through the rehabilitation and recovery of the patient.

A. Hypotheses

C3FIT's *Primary Hypothesis* is that the ISPU model of care will show improved mean level SIS and smRS scores at 12 months compared to the CSC/PSC model of care.

The *Secondary Hypotheses* are:

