C3FIT clinical site eligibility for inclusion is the JC CSC/PSC certification (or operating as such), which ensures that all sites will have well-established in-hospital care delivery programs and documented success in guideline-driven delivery of care that introduces a level of homogeneity among clinical sites. Sites with sufficient volume of stroke admissions were identified with selection was made with special consideration given to sites with populations that include diverse race/ethnic groups. At the patient level, all stroke patients with a stroke diagnosis who reside in a defined geographic region are potential candidates. Though JC CSC/PSC clinical sites tend to be located in largely urban areas, we will include geography in the target population that encompasses the index county and contiguous counties to include both a more diverse and more rural population.

D. Patient Eligibility

Inclusion and Exclusion Criteria are detailed below.

Inclusion Criteria:

- Age 18+.
- Clinical diagnosis of acute stroke with or without brain imaging compatible with intracerebral hemorrhage or ischemic stroke; see ICD 10 codes in Table 4.
- English or Spanish speaking subjects.
- Patient admitted within 7 days of their index stroke event.
- Patient is discharged alive and not to hospice care.
- Patient living at discharge within the geography of recruitment for that C3FIT site.
- Pre-morbid mRS/smRS of 0-1.
- Patient and/or surrogate give consent to participate after an informed consent process.
- Patients who go to rehabilitation inpatient therapy or other care facilities are eligible, as long as they reside in the geographic area of recruitment and do not go to hospice care.

Exclusion Criteria:

- Clinical transient ischemic attack (TIA)³⁸⁻⁴¹ is ***excluded*** even if there is a computerized tomography (CT) or magnetic resonance imaging (MRI) lesion corresponding to the clinical syndrome at presentation.
- Already enrolled or planned enrollment in another clinical trial for which participation in C3FIT would be compromised with regard to follow-up assessment of outcomes or continuation in C3FIT.
- Patients with a planned admission to hospice care prior to consent.
- Patients not anticipated to survive for 1 year due to neurological or other medical status (i.e., advanced cancer, hospice care, heart disease, etc.).
- Patients who in the opinion of the site investigator cannot be involved in follow up care.

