In both CSC/PSC and ISPU Sites, study personnel will be responsible for approaching suspected stroke patients, describing the study, and providing an IRB-approved informed consent process for the patient and caregiver. Admission records will be reviewed frequently by the site personnel, and discharge diagnosis and zip code of residence of all patients admitted with stroke will be identified to determine inclusion.

During hospital discharge or within 5 business days post discharge ideally (to a maximum of 14 total days) patients meeting all inclusion/exclusion criteria for enrollment in C3FIT will be involved in an informed consent process, and once consent is obtained the subject will be given a unique identifier. After consent has been obtained, study personnel will obtain the location to which the patient will be discharged, discharge diagnosis by ICD code, primary and secondary outcomes and other baseline data. Caregivers may be consented at any time during the C3FIT study, but no data will be collected from them until consent is obtained.

In conjunction with our patient and caregiver stakeholders, we will develop and utilize a protocol-driven approach for approaching patients and caregivers about the study and where possible, both patients and caregivers will participate in the consent process. Training on patient identification and a video on the informed consent process will be developed at the Clinical Coordinating Center (CCC) based on the pilot experience. If questions arise from an individual approached for recruitment, our patient/caregiver research partners at each C3FIT Site may be engaged to assist.

Table 5. CSC/PSC Care compared to ISPU Care

Parameter	CSC/PSC	ISPU
Time Focus	Acute care hospital door-to-door and follow-up over 1 year	Continuum of care for 1-year
Goals	Process compliance	
• Patient-centered QOL• Patient centered functional outcome
Measurement	Performance measures	
• Functional outcome
Geography of Care Delivery	
• Hospital• Post-hospital clinic• Home health	
• Hospital• Home- and caregiver/family-based post-stroke care (Stroke Mobile)
Integration with Rehabilitation	
• Discharge summary and clinic follow-up	
• Stroke Connect active in in-patient rehab centers and extended care facilities thru Stroke Mobile

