Time Focus	Acute care hospital door-to-door and follow-up over 1 year	Continuum of care for 1-year
Goals	Process compliance	
 • Patient-centered QOL • Patient centered functional outcome
Measurement	Performance measures	
 • Functional outcome
Geography of Care Delivery	
 • Hospital • Post-hospital clinic Home health 	
 • Hospital • Home- and caregiver/family-based post-stroke care (Stroke Mobile)
Integration with Rehabilitation	
 • Discharge summary and clinic follow-up 	
 • Stroke Connect active in in-patient rehab centers and extended care facilities thru Stroke Mobile
Focus of Modification	Providers	Patient and family
Post-hospital Follow-up	Clinic	Home
Patient/Caregiver/Family-centered Care	No	Yes
Patient-centered Outcome	No	Yes

personnel, and discharge diagnosis and zip code of residence of all patients admitted with stroke will be identified to determine inclusion.

During hospital discharge or within 5 business days post discharge ideally (to a maximum of 14 total days), patients meeting all inclusion/exclusion criteria for enrollment in C3FIT will be involved in an informed consent process, and once consent is obtained the subject will be given a unique identifier. After consent has been obtained, study personnel will obtain the location to which the patient will be discharged, discharge diagnosis by ICD code, primary and secondary outcomes and other baseline data. Caregivers may be consented at any time during the C3FIT study, but no data will be collected from them until consent is obtained.

In conjunction with our patient and caregiver stakeholders, we will develop and utilize a protocol-driven approach for approaching patients and caregivers about the study and where possible, both patients and caregivers will participate in the consent process. Training on patient identification and a video on the informed consent process will be developed at the Clinical Coordinating Center (CCC) based on the pilot experience. If questions arise from an individual approached for recruitment, our patient/caregiver research partners at each C3FIT Site may be engaged to assist.

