## **4. Secondary Outcomes**

### **4.1. Time-to-event secondary outcomes (mortality, recurrent stroke, and rehospitalization)**

The number of days between discharge and death, recurrent stroke or rehospitalization will be calculated, and treatment differences in the times will be assessed using hierarchical proportional hazards models (i.e., using a RANDOM statement for site if conversion, or fixed effect with no conversion). The same incremental modeling approach (crude, adjusted for stroke severity, further adjusted for demographics, and finally adjusted for risk factors) will be employed. It is possible that the number of events may be relatively small (particularly for death and recurrent

stroke), introducing concerns for the use of too many covariates relative to the number of predictors. Should this be the case, a “restricted” number of covariates will be considered, specifically using NIHSS as the single index of severity, using age and race/ethnicity as the indexes of demographics, and hypertension as the single index of risk factors. These will be added in this order up to the point where there are at least 10 events for each factor introduced (i.e., perhaps, not even all these predictors can be considered).

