#### **4.2. Time-at-home**

The proportion of the “time at risk” (defined as the patient being alive and with known status) to be at home will be calculated for each patient, where patients with a no time at risk will be excluded from analysis. Time at home is defined by subtracting time during hospitalization, rehabilitation, skilled nursing from the follow-up time (defined as the time from discharge to last follow-up, death or withdrawal date). Treatment differences in the time-at-home will be assessed in a hierarchical regression model (patients within sites). A 4-level incremental modeling approach like that used for other outcomes will be employed, with the modification that the time at risk will be considered in all models. The first step in considering the time at risk is to assess an interaction with treatment, and should this interaction be significant ( $p < 0.10$ ) the analysis will be stratified and the median value for time at risk. After this determination, the analysis will proceed in a similar manner as other outcomes with the exception that time at risk will be included as a covariate in all models.

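### SAP 4.1 counts survival time from discharge although consent may come up to 14 days later; for mortality, patients should enter the risk set at consent

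*SAP*

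**What the plan says.** SAP 4.1 defines the three time-to-event outcomes from hospital discharge: "The number of days between discharge and death, recurrent stroke or rehospitalization will be calculated". For the analysis, "treatment differences in the times will be assessed using hierarchical proportional hazards models". It says nothing about delayed entry, left truncation or a landmark.

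Consent can come later than that origin. Section 4.F of the ISPU-arm protocol reads "During hospital discharge or within 5 business days post discharge ideally (to a maximum of 14 total days) patients meeting all inclusion/exclusion criteria", and section 4.F of the CSC/PSC-arm protocol gives the same window: "During hospital discharge or within 5 business days post discharge ideally (to a maximum of 14 total days), patients meeting all inclusion/exclusion criteria". Section 4.D of both requires discharge alive and not to hospice. It also excludes "Patients with a planned admission to hospice care prior to consent", which ties one criterion to the consent date. Being alive at consent is not a written criterion, but the consent requirement implies it.

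Section 10.A of both protocols also says that patients are to be approached before they leave hospital and that the consent process starts at admission. Consent after discharge is therefore permitted but is not the only route.

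**The concern.** Take two similar patients who would both die six days after discharge. One is consented in hospital, is in the trial, and the death counts. The other would have been consented on day 8, dies first, and never becomes a participant. Among patients consented after discharge, every one who is analysed has survived to the consent date. Counting their time from discharge puts person-days into the mortality denominator in which no death could have been recorded.

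This has two consequences. Early mortality is too low in any arm that has late-consented patients. If the consent delay differs between arms, the mortality hazard ratio moves as well, and the arm that consents later looks better. Such a difference is possible because sites are randomized and recruiting staff know their arm. Recruitment is also staffed differently: Stroke Central screens the admission logs at ISPU sites and a coordinator does so at CSC/PSC sites. The documents do not say that delays differ, or in which direction.

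**Working it through.** The plan states no event rate, hazard ratio or power for the time-to-event outcomes, so there is no figure of its own to reproduce.

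**From the documents:** origin at discharge (SAP 4.1); consent at most 14 days later (section 4.F of both protocols); planned sample of 1,262 (Protocol Summary).

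**Assumed:** one-year mortality of 10%; a daily hazard in days 1 to 14 that is k = 1, 3, 5 or 10 times the later hazard; late consent spread evenly over days 1 to 14.

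**Step 1. Time affected.** At most 14/365 = 3.8% of the year, and only for patients consented after discharge.

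**Step 2. Share of cumulative hazard in the first 14 days.** f = 14k/(14k + 351), which is 3.8%, 10.7%, 16.6% and 28.5% for k = 1, 3, 5 and 10.

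**Step 3. Understatement of absolute risk.** If everyone consented on day 14, the observed risk would be 1 − S(365)/S(14).
- k = 1: total cumulative hazard is −ln 0.9 = 0.1054, S(14) = exp(−0.0384 × 0.1054) = 0.9960, and the observed risk is 1 − 0.9/0.9960 = 9.6%.
- k = 10: S(14) = exp(−0.2851 × 0.1054) = 0.9704, and the observed risk is 1 − 0.9/0.9704 = 7.3%.

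If half consent late, the observed risk is 9.9% (k = 1) to 9.3% (k = 10).

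**Step 4. Hazard ratio.** I solved the large-sample Cox score equation on a daily grid. Patients are enrolled only if alive on the consent day. Risk time is counted either from discharge (as in SAP 4.1) or from consent. In the 20% v 60% columns, 20% of ISPU and 60% of CSC/PSC patients consent late.

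| k | Equal delays, true HR 1 | 20% v 60%, true HR 1 | 20% v 60%, true HR 0.8 | Entry at consent |
|---|---|---|---|---|
| 1 | 1.000 | 1.009 | 0.807 | true value |
| 3 | 1.000 | 1.025 | 0.820 | true value |
| 5 | 1.000 | 1.039 | 0.831 | true value |
| 10 | 1.000 | 1.070 | 0.856 | true value |

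The equal-delay result holds even if everyone consents on day 14. As an outer bound, all ISPU patients on day 14 against all CSC/PSC patients at discharge gives 0.960, 0.888, 0.827 and 0.706 under a true HR of 1. Nothing in the documents suggests so extreme a split.

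**Hand check.** A late-consented patient loses on average 7.5/14 = 53.6% of the first-fortnight deaths, so HR ≈ (1 − 0.2 × 0.536f)/(1 − 0.6 × 0.536f). For k = 10 this is 0.9695/0.9083 = 1.067, close to 1.070. For k = 1 it is 0.9959/0.9877 = 1.008, close to 1.009.

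**Step 5. Set against sampling error.** With 1,262 patients, 10% mortality and equal arms there are about 126 deaths, and SE(log HR) ≈ 2/√126 = 0.178 before clustering. ln 1.070 = 0.068 is 0.38 of one SE, and ln 1.009 = 0.009 is 0.05 of one SE.

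**The case against.** The strongest reply is that both arms share one window and equal delays leave the hazard ratio untouched. Consent is also meant to begin in hospital, and the shift under a moderate imbalance is well inside sampling error for a secondary outcome. All of that stands, and it limits the point to a minor one. It does not remove the understated early mortality, which needs no imbalance, and it gives no reason to prefer a risk set that includes impossible person-time.

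Four stronger readings are tempting, and the documents do not support them.

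- A reader might infer that the discharge origin by itself biases the treatment comparison. It does not. Delay, or selection during the gap, must differ by arm, and no delay data are given.
- A reader might infer the same immortal time for recurrent stroke and rehospitalization. No criterion requires freedom from either before consent, and Table 1 does not limit capture to events after consent. A serious event in the gap could lead an investigator to judge a patient unfit for follow-up or unlikely to survive the year. A readmitted patient could equally reappear on the screened admission logs and be approached. The direction is unknown.
- A reader might see conflicting time origins, because the Protocol Summary says "Patients will be followed at the site level for one year after enrollment". That sentence gives the length of site follow-up, not an analysis origin. SAP section 1 places the assessment 12 months after discharge, in line with 4.1.
- A reader might want the origin in SAP 4.2 moved too, since follow-up there is "defined as the time from discharge to last follow-up, death or withdrawal date". Starting at consent would discard early rehabilitation and skilled-nursing days, which are part of what that outcome measures.

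**Conclusion.** The point holds for mortality. SAP 4.1 gives late-consented patients up to 14 days of follow-up in which death could not be observed, and early mortality is understated as a result. The hazard ratio is biased only if consent delays differ by arm: by about 1% to 7% for an assumed 20% against 60% consented late, and by nothing if delays match. These sizes rest on an assumed 10% one-year risk, assumed early hazards and an assumed consent split, none of which the documents give. That the truncated time exists is certain. Whether the hazard ratio is biased, and in which direction, cannot be told from the plan. For recurrent stroke and rehospitalization the remaining issue is that the SAP does not say how events before consent are handled. The severity is minor, because this is a secondary outcome with a small expected effect.

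**What to change.** In SAP 4.1, keep days since discharge as the time scale. For mortality, let each patient enter the risk set at the later of discharge and consent (for example ENTRY= in PHREG), after checking that the software accepts this together with the random site effect. For recurrent stroke and rehospitalization, keep the discharge clock as the main analysis, state whether events before consent count, and run the delayed-entry model as a sensitivity analysis. Making it the main analysis would drop known events or relabel a second event as a first. Tabulate days from discharge to consent by arm. Leave the SAP 4.2 origin at discharge.

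The cost is a few sentences and one table. At most 14 days of mortality follow-up per late-consented patient leaves the analysis, and no deaths are lost, since none can occur before consent among enrolled patients. It assumes that the consent date can be taken from the signed forms, which both protocols say are kept at the sites.

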#### **4.2. Time-at-home**

The proportion of the “time at risk” (defined as the patient being alive and with known status) to be at home will be calculated for each patient, where patients with a no time at risk will be excluded from analysis. Time at home is defined by subtracting time during hospitalization, rehabilitation, skilled nursing from the follow-up time (defined as the time from discharge to last follow-up, death or withdrawal date). Treatment differences in the time-at-home will be assessed in a hierarchical regression model (patients within sites). A 4-level incremental modeling approach like that used for other outcomes will be employed, with the modification that the time at risk will be considered in all models. The first step in considering the time at risk is to assess an interaction with treatment, and should this interaction be significant ( $p < 0.10$ ) the analysis will be stratified and the median value for time at risk. After this determination, the analysis will proceed in a similar manner as other outcomes with the exception that time at risk will be included as a covariate in all models.

#### **4.3. Depressive symptoms**

Depressive symptoms will be assessed using the PHQ-9 dichotomized at scores of 0 to 9 versus 10 and above (note that if fewer than 10% of patients present with depressive symptoms the score will be dichotomized at the median). The analysis of this outcome will then follow the approaches described above for dichotomous outcomes measured only at follow-up (i.e., adherence to exercise and diet guidelines).

#### **4.4. Caregiver strain index (mCSI)**

The (modified) CSI is assessed at the 3, 6 and 12-month follow-up (not at month 0) and is a 13-item scale, producing a score from 0 to 26. The analysis will focus on the difference at month 12, but will use a mixed model approach incorporating data from the 3 and 6 month timepoints (note that without data at month 0, change from discharge is not defined). The analysis will follow the approaches for the primary outcome with the 4-level incremental models.

#### **4.5. Perceived level of support**

The perceived level of support was assessed through the study at the 3, 6 and 12-month visit and is measured on 5 point scale. The differences in the mean score at each follow-up time will be assessed using a mixed model in a manner similar to the mCSI above.

